Programming of the device is completed using the MAX Programming Interface and MAESTRO System Software. The MAESTRO software is used for different intraoperative and postoperative purposes for the MED-EL Cochlear Implant System. It contains the implant Telemetry, Fitting and Configuration of all available audio processors, ART (Auditory nerve Response Telemetry), ESRT (Electrically Evoked Stapedius Reflex Threshold), EABR (Evoked Auditory Brainstem Response) and Audiogram functions. The MAESTRO software is an external component of the MED-EL Cochlear Implant System and is intended to be used in a clinical or office environment by persons adequately skilled and trained to perform all intended tasks and with patients who received one of the intended MED-EL Cochlear implants.

For the pediatric population, the MED-EL Synchrony cochlear implant is currently indicated for children 12 months to 17 years and 11 months of age, who have bilateral sensorineural hearing impairment and obtain limited benefit from appropriately fitted binaural hearing aids. In this study, the use of this system is considered investigational because it will be used for children who have unilateral moderate to profound sensorineural hearing loss rather than bilateral profound sensorineural hearing loss.

5) Study Duration

- a) Enrollment Period
4 years

- b) Study Timeline

Each participant's involvement will last approximately 2.5 years, including: candidacy evaluation, preoperative evaluation, surgical procedure, initial activation of the external speech processor, therapy schedule, and post-initial activation evaluations (3, 6, 9, 12, 18 and 24-months post-initial activation).

- c) Study Endpoint

The study endpoint for each participant is the 24-months post-initial activation interval.

6) Methods

- a) All procedures will be conducted by UNC investigators, including board-certified otologists, audiologists, and speech-language pathologists. Fully informed consent will be obtained from all participants and/or their parents.
- b) Participants must meet the following inclusion criteria and not exhibit any of the exclusion criteria.
 - i) Inclusion Criteria
 - (1) Unilateral moderate-to-profound sensorineural hearing loss.
 - (a) Unaided residual hearing thresholds that yield a PTA at frequencies 500Hz, 1K Hz and 2K Hz of ≥ 70 dB HL in the ear to be implanted. It is possible that subjects may have hearing at other frequencies not included in this average.

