Appendix A graphically depicts the timeline and associated measures

i) **Candidacy Evaluation.** This interval may overlap with the Preoperative Evaluation interval.

- (1) Audiologic Evaluation
 - (a) Unaided air- and bone-conduction thresholds in both ears
 - (i) Air-conduction assessed with inserts
 - (b) Unaided word recognition in both ears
 - (i) Measured with recorded CNC words (50-word list)
 - (ii) Masking provided when appropriate (Turner, 2004)
 - (c) Tympanometry in both ears
 - (d) Aided word recognition in the affected ear
 - (i) Measured with recorded CNC words (50-word list)
 - (ii) Masking applied to the contralateral ear
 - (e) Completion of all questionnaires
 - (f) Determine if potential participant meets candidacy criteria
- (2) Speech-language and psycho-education evaluation
 - (a) Oral Written Language Scale (OWLS-II)
 - (b) Goldman Fristoe Test of Articulation
 - (c) Leiter-R
- (3) Medical Evaluation
 - (a) Determine if potential participant is healthy enough to undergo cochlear implantation
 - (b) Associated imaging studies
 - (c) Discussion of alternative treatment options
 - (d) Determine if potential participant meets candidacy criteria
- (4) Informed Consent
 - (a) Review and discussion of consent form
 - (b) Provide time for participant and/or parents to review consent form and ask questions
 - (c) Provide participant and/or parents with a signed copy of the completed consent form

The Preoperative Evaluation will be completed within 6 months of the surgery date.

- (1) Audiologic Evaluation
 - (a) Obtain a case history, including but not limited to:
 - (i) Onset of hearing loss
 - (ii) Stability or progression of sensorineural hearing loss
 - (iii) Suspected etiology of hearing loss

- (b) Unaided air- and bone-conduction thresholds in both ears assessed with insert phones
- (c) Unaided word recognition with CNC words in both ears
 - (i) Measured with recorded CNC words (50-word list)
 - (ii) Masking provided when appropriate (Turner, 2004)
- (d) Tympanometry in both ears
- (2) Speech-language and psycho-education evaluation
- (3) Parental Questionnaires – will serve as anchor point for future questionnaires
- (4) Counseling of parents on cochlear implant external technology, realistic expectations, study test battery, and postoperative timeline
- (5) Medical Evaluation
 - (a) Participants will undergo a medical assessment and review of medical history
 - (b) Associated imaging studies

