- (d) Assessment of hearing in contralateral ear
- (e) Mapping of the external speech processor

(7) Nine-Months Post-Initial Activation

- (a) Localization assessment
- (b) Parental questionnaires - anchored to prior questionnaires
- (c) Speech perception with the cochlear implant via direct input to processor
- (d) Mapping of the external speech processor

(8) Twelve-Months Post-Initial Activation

- (a) Hearing in noise assessment
- (b) Parental questionnaires - anchored to prior questionnaires
- (c) Speech perception with the cochlear implant via direct input to processor

- (d) Mapping of the external speech processor
- (e) Assessment of hearing in contralateral ear
- (f) Speech-Language evaluation

(9) Eighteen Months Post-Initial Activation

- (a) Localization assessment
- (b) Parental questionnaires - anchored to prior questionnaires
- (c) Speech perception assessed with the cochlear implant via direct input to processor
- (d) Mapping of the external speech processor

(10) Twenty-four Months Post-Initial Activation

- (a) Localization assessment
- (b) Hearing in noise assessment
- (c) Parental questionnaires - anchored to prior questionnaires
- (d) Speech perception with the cochlear implant via direct input to processor
- (e) Mapping of the external speech processor
- (f) Assessment of hearing in contralateral ear
- (g) Speech-language evaluation

d) Test Battery

The following test battery will be completed at various assessment intervals (preoperative, and at 3, 6, 9, 12, 18, and 24 months postoperatively) as defined in 6.iv. All assessment and mapping will be conducted at the Children's Cochlear Implant Center at UNC or at the Carolina Crossing research lab by board-certified audiologists.

i) Hearing Assessment

- (1) Air-conduction thresholds in both ears
 - (a) Air-conduction assessed with insert phones
 - (b) Assess bone-conduction thresholds if there is a PTA shift of >15 dB as compared to the previous interval
- (2) Aided thresholds with the external speech processor on will be measured using warble tones
 - (a) Frequencies assessed: 250-8000 Hz
 - (b) Masking presented to the contralateral ear (Turner, 2004).

ii) Tympanometry for each ear

iii) Speech Perception Measures in Quiet in ear of implant

- (1) Recorded materials will be presented at a comfortable listening level via direct input
- (2) Speech perception materials will be presented in a hierarchy, with advancement to the next test contingent on performance on the previous test

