- b) A single-subject design will be utilized, where each participant serves as his or her own control, for analysis of objective and subjective results. A single-subject design was chosen in order to accommodate the heterogeneity that is well known to characterize auditory prosthesis research. Repeated-measures ANOVA will be calculated with a p-value of ≤ 0.05 for statistical significance. Statistical analysis will be conducted with SPSS software.
 - i) Comparison of aided speech perception performance to the baseline condition (either unaided or aided with hearing aid, depending on the participants residual hearing) and in the post-initial activation intervals to evaluate trends over time
 - ii) Comparison of localization abilities to the baseline condition (either unaided or aided with hearing aid, depending on the participant's residual hearing) and in the post-initial activation intervals to evaluate trends over time
 - iii) Compute the overall rms error, random error, constant error, and adjusted constant error, as described by Grantham et al (2007)
 - iv) Comparison of subjective report scores in the post-initial activation intervals. Group means compared with Bonferroni's adjusted t tests or repeated-measure ANOVAs. Pearson's correlations will be used to analyze relationships between variables.
 - v) Subjective report scores will be compared to norms for this test. Group means compared with Bonferroni's adjusted t tests or repeated-measure ANOVAs. Pearson's correlations will be used to analyze relationships between variables.
- c) The incidence of interference between ears will be assessed at the 6,12 and 24 month post initial stimulation visit by comparing the speech perception performance in the 0° azimuth conditions for the contralateral ear only versus cochlear implant + contralateral ear conditions for each participant, as well as the individual's subjective report.

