A sample size of 20 participants was selected due to known variability in conventional cochlear implant recipient outcomes and to allow for possible dropouts (approximately 20%). A comparable study, Hansen, Gantz & Dunn (2013) evaluated 29 adult cochlear implant participants with UHL, which included etiologies of sudden sensorineural hearing loss, Meniere's disease, and vestibular schwannoma. Authors reported a high degree of variability in their sample. This project will not enroll all of the etiologies included in the Hansen, Gantz & Dunn (2013) analysis (such as, Meniere's Disease with intractable vertigo or history of vestibular schwannoma), therefore a smaller sample size was selected. The inclusion/exclusion criteria associated with this study, as compared to the heterogeneity of the Hansen, Gantz, & Dunn (2013) subject sample, will allow for more generalized comments about subjective and objective outcomes of cochlear implantation in pediatric cases of UHL.

If needed, statistical consultation will be sought from the North Carolina Translational and Clinical Sciences Institute (TraCS) or UNC Odum Institute.

9) Endpoints

- a) Safety endpoint
 - i) The primary safety endpoint is the evaluation of Adverse Events. All Adverse Events will be reported to the UNC IRB. If the UNC IRB or study investigators deem an Adverse Event unacceptable, then this would result in termination of the study.
- b) Primary effectiveness endpoint
 - i) The primary effectiveness endpoint is the comparison of speech perception, localization abilities and/or subjective report when the cochlear implant is on versus the preoperative unaided condition as well as changes in quality of life as measured by the Speech, Spatial and Qualities of Hearing Scale (SSQ), (Gatehouse & Noble 2004), the modified Bern SSD Questionnaire, (Kompis, Pfiffner, Krebs & Caversaccio , 2011) and the PedsQL Multidimensional fatigue scale (Varni, Limbers & Burwinkle, 2007).

10) Risk Analysis

- a) Potential risks to cochlear implantation

The following are risks associated with the MED-EL Synchrony implant, which is included in the device description:

1. Loss of residual hearing
2. Dizziness
3. Increased vertigo
4. Delay of healing of the scar
5. Impairment of the sense of taste

6. Potential for swallowing difficulties
7. Numbness
8. Increased tinnitus
9. Stimulation of the facial nerve
10. Temporary pain and uncomfortable sounds during stimulation

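### The questionnaire analysis fixes neither the test nor the Bonferroni family, and as written it omits the preoperative comparison that the primary effectiveness endpoint calls for

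*Combined protocol and SAP*

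**What the plan says.** Section 8.b sets a general rule for objective and subjective results: "Repeated-measures ANOVA will be calculated with a p-value of ≤ 0.05 for statistical significance". Items iv and v then reopen the choice for questionnaires by allowing Bonferroni "adjusted t tests or repeated-measure ANOVAs". Item iv describes its task as "Comparison of subjective report scores in the post-initial activation intervals". Item v repeats the same pair of tests for a comparison with norms. Neither item says which test decides, over what set of comparisons the Bonferroni adjustment runs (visits, pairs, domains or questionnaires), or how departures from sphericity are handled.

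The visit schedule in 5.b lists "post-initial activation evaluations (3, 6, 9, 12, 18 and 24-months post-initial activation", which makes six visits. The preoperative evaluation in 6.c adds a parental questionnaire that "will serve as anchor point for future questionnaires", and the later forms are "anchored to prior questionnaires".

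The primary effectiveness endpoint in 9.b.i compares the implant-on state with the unaided state before surgery. It counts subjective report as one possible route and adds changes on the SSQ, the modified Bern questionnaire and the PedsQL fatigue scale. No analysis visit is named there. Section 5.c, under Study Duration, states: "The study endpoint for each participant is the 24-months post-initial activation interval". Section 8 ends its sample-size text with: "If needed, statistical consultation will be sought".

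**The concern.** There are two problems.

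**The comparison.** The endpoint is change from before surgery. Item iv, read literally, tests for differences among the 3- to 24-month scores. If children improve by 3 months and hold the gain, those six means are equal. The ANOVA and the t tests would then reject only at about their error rate, however large the gain from the preoperative form.

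**The open choice.** If two tests of the same question are available and either may count, the chance of a false positive exceeds that of each test alone. Scores from visits 3 to 24 months apart may also be more alike when the visits are close together. That breaks sphericity and inflates an uncorrected repeated-measures F test. The Bonferroni route has a different weakness: the more comparisons in its undefined family, the less power remains for any one of them.

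This matters because subjective report can carry the effectiveness conclusion in 9.b.i, and the claim in 7.a.ii rests on parental perception.

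**Working it through.** **Inputs from the documents.** Alpha 0.05 (8.b; two-sided assumed, as sidedness is not stated). 20 children enrolled (6.b.iii) and about 20% dropout (section 8), so 20 × 0.8 = 16 completers. Six post-activation visits give 6 × 5 / 2 = 15 pairs. Adding the preoperative form gives 7 × 6 / 2 = 21 pairs, of which 6 are contrasts against preoperative.

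**Not in the documents.** Power, effect size, standard deviation and between-visit correlations are all absent. The sample size of 20 therefore cannot be reproduced from a power calculation; only the dropout arithmetic can be checked. Everything below rests on stated assumptions.

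**1. What item iv tests.** Let the mean score be μ0 before surgery and μ3, …, μ24 afterwards. Item iv's null hypothesis is μ3 = μ6 = μ9 = μ12 = μ18 = μ24. The endpoint in 9.b.i concerns the difference between a post-activation mean and μ0. If all six post-activation means equal μ0 + δ, item iv's null is true for any δ, and none of the 15 pairs contains μ0.

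**2. Error rate per score if either test may count.** 20,000 null simulations per scenario, with n = 16 and 20 and with six and seven visits. Correlations were equal (0.5 or 0.7) or decaying (0.5 to 0.99 per 3 months). Ranges run across all scenarios.

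| | Equal correlations (sphericity) | Decaying correlation |
|---|---|---|
| Uncorrected ANOVA alone | 4.8–5.2% | 6.2–10.9% |
| Uncorrected ANOVA or any Bonferroni pair | 6.5–7.3% | 7.6–12.0% |
| Uncorrected ANOVA or any Bonferroni contrast with the first visit | 7.2–7.7% | 8.2–12.4% |
| Greenhouse-Geisser ANOVA or any Bonferroni test | 5.4–6.4% | 5.7–7.0% |

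With one test fixed in advance, the error is 2.9–5.1% for Greenhouse-Geisser ANOVA and 3.0–4.4% for Bonferroni t tests.

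To separate the causes, take the worst case (n = 16, seven visits, correlation 0.99 per 3 months). The uncorrected ANOVA alone gives 10.9%. Adding the pairs gives 12.0%, and adding first-visit contrasts instead gives 12.4%. The free choice contributes about 1 to 1.5 points; the rest of the excess over 5% is lost sphericity.

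**3. Power for one paired contrast under Bonferroni.** Two-sided paired t test: power = P(|T| > t(1 − α/2m; n − 1)), where T is noncentral t with n − 1 degrees of freedom and noncentrality d√n. The standardised change d is chosen to give 80% at m = 1: d = 0.749 for n = 16 (noncentrality 3.00) and d = 0.660 for n = 20 (2.95).

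| Family size m | α/m | Critical t, n = 16 | Power, n = 16 | Power, n = 20 |
|---|---|---|---|---|
| 1 planned contrast | 0.05 | 2.131 | 80% | 80% |
| 6 contrasts against preoperative | 0.00833 | 3.036 | 51% | 52% |
| 15 pairs (post-activation only) | 0.00333 | 3.484 | 36% | 38% |
| 21 pairs (with preoperative) | 0.00238 | 3.648 | 31% | 33% |

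**The case against.** **The lead sentence of 8.b already names repeated-measures ANOVA for subjective results, and each child is described as his or her own control.** This is a fair default reading, but items iv and v override it for questionnaires, and item iv restricts the visits.

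**The error-rate excess is small and rests on assumptions.** This stands in part. A reader might infer that the *or* pushes the real error rate to 12%. The documents do not support that: they give no correlations, and values near 12% need strongly decaying correlation and an uncorrected ANOVA. Anchoring a form to earlier ones does not establish that errors accumulate over visits.

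**The plan does not specify all-pairs testing and states no power.** This stands. A reader might infer that the plan's power falls from 80% to 31%. The 80% is assumed, and 31% needs all 21 pairs and 16 completers. Item iv's literal scope gives 15 pairs and 36%.

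**Section 5.c does not make 24 months the analysis time.** This also stands. It sits under Study Duration and most naturally marks the end of each child's participation. Choosing 24 months for the contrast is a proposal, compatible with 5.c but not dictated by it.

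**Consultation *if needed* does not show that the test would be chosen after seeing results.** Correct; the sentence is silent on timing. The point is only that nothing in the plan prevents it.

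**The Bern form may have no clear preoperative meaning**, since it rates the benefit of a hearing technology. The fix has to allow for this.

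**This is a feasibility study.** Section 2 says so, but the same sentence sets out to demonstrate effectiveness.

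**Conclusion.** The concern holds in a bounded form. The firmest part needs no assumption about correlation: item iv, followed literally, does not test the preoperative comparison in 9.b.i and cannot detect a benefit that is complete by 3 months and then stable. The test and the Bonferroni family are also not fixed.

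On assumed correlations, the per-score error if either test may count is about 6.5 to 7.5% under sphericity, about 8 to 12% with decaying correlation and no correction (most of the upper end being sphericity inflation), and about 5.5 to 7% with Greenhouse-Geisser. These rates are per score; testing several scores without adjustment would raise the study-wide rate.

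If Bonferroni were run over all pairs, an assumed 80% power would fall to about 31 to 38%. Over six contrasts against preoperative it would be 51 to 52%. These power figures describe possible readings of an undefined family, not the plan's stated power.

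**What to change.** **In 8.b.iv:**
- Prespecify one paired contrast, preoperative to 24 months, with a 95% CI, for each questionnaire score that has a meaningful preoperative value. List those scores and say how the Bern form is treated.
- State how 0.05 is shared across the listed scores, for example by Holm's procedure. The plan has no such allotment at present.
- Keep repeated-measures ANOVA, with the Greenhouse-Geisser correction, as a secondary description of the time course.
- Remove the *or* and state that all pairs of visits will not be tested.

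**In 8.b.v:** name one method for the comparison with norms, for example a one-sample comparison at 24 months with a CI.

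The cost is a change of SAP wording. No visit, procedure or sample size changes, because the preoperative and 24-month forms are already collected. The small downside is that the other visits become descriptive.

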
- (2) This study seeks to enroll twenty (20) participants.

c) Timeline

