
- (3) Test materials to include:
 - (a) 3 subtests of Early Speech Perception Test (ESP), if > 70% then,
 - (b) CNC words
- iv) Speech Perception in Noise in binaural condition (6, 12, and 24 months post-initial activation)
 - (1) Speech processor on
 - (a) Listening conditions, noise orientation
 - (i) Speech and noise at 0° azimuth.
 - (ii) Speech 0° azimuth and noise to implanted side
 - (iii) Speech 0° azimuth and noise to contralateral ear
 - (b) Speech perception materials
 - (i) BKB-SIN
 - (2) Speech processor off
 - (a) Listening conditions, noise orientation
 - (i) Speech and noise at 0° azimuth.
 - (ii) Speech 0° azimuth and noise to implanted side
 - (iii) Speech 0° azimuth and noise to contralateral ear
 - (b) Speech perception materials
 - (i) BKB-SIN
- v) Sound Field Localization Measures (3, 9, 18, and 24 months post-initial activation)
 - (1) Postoperative aided sound field assessment will be measured in the free field with the Sonnet speech processor turned on and with the processor turned off.
 - (2) Testing will be completed in a double-walled soundproof booth. Eleven loudspeakers are arrayed in a 180-degree arc, with speakers evenly spaced at 18-degree intervals. Speakers are mounted at ear level, all spaced approximately 1-meter from the listener.
 - (3) The stimulus is a 200-ms speech-shaped noise, presented at 70-dB SPL. The speaker used to present the stimulus is randomly selected from the 11 alternatives on each trial, with the caveat that each speaker is used 3 times during a block of 33 trials. At least one block of 33 trials will be obtained in each condition (with and without the processor turned on).
 - (4) The listener faces the middle speaker prior to and during stimulus presentation. The task is to identify the source of the noise. Feedback is provided during instruction and training trials, but not during data collection.
 - (5) Listening Conditions
 - (a) Cochlear implant speech processor off at the 3, 9, 18 and 24 month intervals
 - (b) Cochlear implant speech processor on at the 3, 9, 18 and 24 month intervals

- (6) Performance is analyzed by computing the normalized RMS error, a metric that characterizes a listener's ability to discriminate between sound source locations.
- (7) These procedures have been used successfully to test children as young as 4 years of age.

vi) Parent questionnaires

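### Repeated-measures ANOVA with no missing-data method drops any child with a missed test: the plan's own dropout allowance leaves 16 of 20, and missed visits would leave fewer

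*Combined protocol and SAP*

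**What the plan says.** Section 8.b (Statistical Analysis) sets the method: "Repeated-measures ANOVA will be calculated with a p-value of ≤ 0.05 for statistical significance". It adds: "Statistical analysis will be conducted with SPSS software". No SPSS procedure is named. Items 8.b.i and 8.b.ii apply this to speech perception and localization, against baseline and across the post-activation intervals. For the questionnaires, items 8.b.iv and 8.b.v leave a choice: "Group means compared with Bonferroni's adjusted t tests or repeated-measure ANOVAs".

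The sample size paragraph that closes section 8 justifies 20 children by the variability of implant outcomes and "to allow for possible dropouts (approximately 20" per cent). It gives no effect size, SD or power.

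Section 6.d places the test battery at "preoperative, and at 3, 6, 9, 12, 18, and 24 months postoperatively". Within that, section 6.c.iv schedules quiet speech and questionnaires at all six post-activation visits, localization at four (3, 9, 18 and 24 months) and hearing in noise at three (6, 12 and 24 months).

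Section 6.d.iii makes the CNC test conditional on an easier one: "3 subtests of Early Speech Perception Test (ESP), if > 70% then" CNC words follow.

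The documents contain no analysis set, missing-data rule, imputation, mixed model, sensitivity analysis or expected rate of missed tests.

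**The concern.** Conventional repeated-measures ANOVA needs a full row of scores for each child. A child who misses one of six questionnaires, or leaves after 18 months, is removed from that outcome's analysis completely. In a surgical study of 20 young children, that discards data that were costly to obtain.

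Missed scores are foreseeable from the plan itself:

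- Dropout of about 20% is expected.
- A child who does not pass ESP at 3 months has no CNC score at that visit, and so leaves the whole CNC ANOVA even if every later CNC score exists.
- Implantation is allowed from 3 years 6 months, while section 6.d.v reports the localization procedure as successful from age 4. A child at the lower age limit would be about 3 years 10 months at the 3-month test.
- Section 10.b lists fatigue during follow-up assessment as a risk.

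Two things are at stake: precision, and whether the children left in the analysis still represent those enrolled.

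**Working it through.** **1. The plan's own figure.** 20 × (1 − 0.20) = 16, and 16 / 0.80 = 20. This step is consistent. The 20 itself cannot be derived, because no effect size, SD or power is given.

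**2. Complete cases by outcome.** Let m be the chance that a remaining child misses a given test, independently across visits, and k the number of post-activation visits for the outcome. Expected complete cases = 16 × (1 − m)^k. The documents give no m, so a range is shown.

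| Outcome | k | m = 2% | m = 5% | m = 10% |
|---|---|---|---|---|
| Quiet speech; questionnaires if ANOVA is used | 6 | 14.2 | 11.8 | 8.5 |
| Localization | 4 | 14.8 | 13.0 | 10.5 |
| Speech in noise | 3 | 15.1 | 13.7 | 11.7 |

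For example, 16 × 0.95^6 = 11.8. If the baseline score can also be missed, the six-visit row becomes 13.9, 11.2 and 7.7 (k = 7). The extra CNC loss from the ESP gate is not included.

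For comparison, a mixed model keeps every child with usable data. At m = 5%, 16 × 0.95 = 15.2 children would be observed at 24 months, and those who left would still contribute their earlier visits.

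**3. Precision.** The yardstick is a paired t test, two-sided 5% (the plan does not state sidedness) with 80% power. The detectable effect is the d (mean change divided by SD of change) at which a non-central t with n − 1 degrees of freedom and non-centrality d√n gives 80% power.

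| n | Detectable d | Standard error relative to n = 20 |
|---|---|---|
| 20 | 0.66 | 1.00 |
| 16 | 0.75 | √(20/16) = 1.12 |
| 12 | 0.89 | √(20/12) = 1.29 |

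The step from 20 to 16 is dropout that the plan already expects. The step below 16 comes from deleting children who stayed but missed a test.

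**4. Selection.** All inputs here are assumptions.

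- Simulations used a 24-month gain of 2.0 SD and about 18% dropout driven by the previous score. Complete-case bias was 0 under compound symmetry. With random slopes it was +0.02 to +0.04 SD under one set of parameters and +0.05 to +0.10 SD under another, which is 1% to 5% of the gain.
- A simple bound: if 20% leave and leaving has correlation ρ with a child's own gain, the mean among those who stay is too high by ρ × φ(z₀.₂₀) / 0.80 = ρ × 0.280 / 0.80 = 0.35ρ, in SDs of change. That is 0 at ρ = 0, about 0.18 at ρ = 0.5, and 0.35 if exactly the worst 20% leave.

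Neither calculation models the ESP gate.

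**The case against.** The strongest reply has four parts.

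First, a reader might infer that the plan will analyse only about 12 children. The documents do not support that. Their figure gives 16; 12 needs a miss rate of 4.7% at each of six visits, and no rate is stated. Inclusion criterion 10 also asks parents to commit to the evaluation schedule. This part stands, which is why a range by outcome is given.

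Second, the plan does not say that all visits enter one ANOVA, and the questionnaires may be analysed by t tests, which need not delete across visits. A paired comparison at 24 months alone would keep about 15. This stands for the questionnaires. For speech and localization the plan names only ANOVA and asks for trends over time, and the usual implementation deletes any incomplete child.

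Third, a reader might infer that the estimate is biased toward children who do well. That is not shown. Section 10.c foresees children who stop using the implant, but stopping use is not leaving the study. The one specific withdrawal trigger in section 13.b is deterioration of the better ear. That section does characterize withdrawals partly by test performance and device use, so a link with benefit is plausible, but its size and direction are unknown.

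Fourth, if the gain really were 2.0 SD, a complete-case estimate with a simulated SD of 0.27 would lie about seven standard errors from zero (2.0 / 0.27 = 7.4), and the lost children would change no conclusion. That is fair for a large effect. It does not cover outcomes with smaller gains, and the plan states no expected effect for any outcome.

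**Conclusion.** The concern holds as a weakness of method. The plan pairs an analysis that, run conventionally, needs complete rows with an expected 20% dropout and no missing-data method. On its own figure, 16 of 20 children remain. Below that, the count depends on an assumed miss rate: over 2% to 10% per visit it runs from about 15 (noise, 2%) to about 8 or 9 (six-visit outcomes, 10%). The detectable paired effect rises from 0.66 SD at 20 children to 0.75 at 16 and 0.89 at 12.

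Loss of precision is the firm part. Selection toward better performers is a risk: zero if dropout is unrelated to growth and small in the simulations described. CNC is the exception that needs its own attention, because the plan itself withholds the test from children who perform poorly on ESP. This calls for a change to the analysis plan. It does not show that the trial would reach a wrong conclusion.

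**What to change.** In section 8.b, replace repeated-measures ANOVA with a linear mixed model fitted by REML (SPSS MIXED) to all observed visits:

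- Visit is a categorical fixed effect, with processor on/off and its interaction with visit where both conditions are tested.
- Within-child correlation is modelled. With so few children, use a structured form such as a random intercept and slope: an unstructured matrix over seven time points has 7 × 8 / 2 = 28 parameters. This also removes the need for sphericity across unequally spaced visits.
- The 24-month contrast is reported with its 95% CI.

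Two additions are needed because the model alone does not cover them:

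- State how a CNC test not given because of the ESP gate is scored or analysed, for example at the floor of the scale or through an ordered ESP/CNC outcome. A model of CNC alone does not make this missingness ignorable.
- Add a sensitivity analysis for dropout related to poor benefit. A simple bound gives leavers no gain: with 4 of 20 leaving, the mean gain becomes 16/20 = 80% of that among those who stay.

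Complete-case ANOVA may stay as a secondary check, but it does not serve as that sensitivity analysis.

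The cost is plan wording and a little more modelling, with the same data and software. The model relies on data being missing at random and on its covariance assumption.
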